## 5. METHODS

[figure not shown]
### 5.1 Study procedures

#### 5.1.1 Patient selection

During the study period, all referrals for FDG-PET/CT scans in the NM department in Isala will be evaluated by one of the investigators. Based on inclusion and exclusion criteria, the investigator makes an initial selection of patients suitable for this study. Each referral that meets the inclusion criteria will be listed. For these selected patients, we plan a informed consent talk of around 15 minutes with a NM physician, physician assistant or one of the investigators. This talk takes place prior to the first clinical FDG-PET/CT scan. More details on the informed-consent procedure are described in section 8.2 Recruitment and consent.

#### 5.1.2 FDG injection (clinical procedure)

All FDG-PET/CT scans for this study will be acquired on the NM department in Isala (Zwolle). Before acquisition, patients have to be at least 6 hours sober. Before intravenous injection of the radiotracer FDG (GE Healthcare, radiopharmacy, Zwolle), blood glucose levels will be measured to ensure a value below 15 millimol/L. Depending on patients' body weight, 185-500 megabecquerel (MBq) of FDG will be administered (Figure 4).

**Figure 4: Dose-scan time protocol for the conventional PET/CT system, based on patients' body weight (in kilogram).** For patients with a body weight up to 80 kilogram, PET acquisition time is 1 minute per bed position. PET acquisition time is 2 minutes per bed position for patients with a body weight from 81 kilogram. On average 11 bed positions are required to cover the whole-body region.

#### 5.1.3 First PET/CT acquisition

Sixty minutes after FDG tracer injection, a standard clinical whole-body PET/CT scan is performed on the conventional or digital PET/CT scanner. (As mentioned in the study design, the PET scan order is randomized per week). For the first scan, the acquisition times are 1 and 2 minutes per bed position for patients with body weight up to 80 kilogram and from 81 kilogram respectively. To cover the whole-body region, on average 11 bed positions are required. This results in total PET

acquisition times of approximately 11 and 22 minutes for patients with body weight  $\leq 80$  kg and  $> 80$  kg respectively. Furthermore, attenuation CT acquisition takes around 5 minutes in all patients. Moreover, for many patients an additional diagnostic contrast-enhanced CT scan is acquired on the clinical PET/CT system with a total procedure time of approximately 15 minutes.

#### **5.1.4 Second PET/CT acquisition (study procedure)**

Consecutively after the first PET/CT scan, an additional PET/CT scan is acquired on the second PET/CT system. To minimize the decrease in FDG present in the human body when performing the second PET/CT scan, the time between first and second PET/CT scan should be kept as short as possible. However, the amount of FDG present in the human body during the second PET/CT scan will be less as compared to the first PET/CT scan. Therefore, the acquisition time for second PET/CT scanning will equal to first PET/CT scan, plus a compensation for the radioactive decay. Due to differences in PET acquisition times and the acquisition of a diagnostic CT scan, there will be differences in delay time between patients. In general, patients can be divided in four groups for expected delay:

1. Patient bodyweight  $\leq 80$  kg and no diagnostic ceCT: delay  $\approx 21$  minutes
2. Patient bodyweight  $> 80$  kg and no diagnostic ceCT: delay  $\approx 32$  minutes
3. Patient bodyweight  $\leq 80$  kg and a diagnostic ceCT: delay  $\approx 36$  minutes
4. Patient bodyweight  $> 80$  kg and a diagnostic ceCT: delay  $\approx 47$  minutes

FDG has a half-life of 110 minutes. Using the formula for radioactive decay  $N(t) = N(0) \cdot 0.5^{T/T_{0.5}}$ , the percentage of FDG after the delay can be calculated. The correction factor is determined by calculating the inverse of the percentage of FDG, present after the delay. Based on this correction factor, the total acquisition time for the second PET/CT system can be calculated. Table 2 provides an indication of the scan times required for digital PET/CT scanning. As can be seen in this table, patients' bodyweight ( $\leq 80$  kg or  $> 80$  kg) is the main predicting factor whether the acquisition time on second PET takes approximately 20 minutes or approximately 35 minutes. Based on this estimation, we expect that the additional time for patients participating in this study will typically be 25 minutes but will not take more than 40 minutes.

**Table 2: Indications of total scan time on second PET/CT system, based on expected delays in four groups of patients.** The total scan time on second PET/CT includes the time for PET acquisition (with 11 bed positions (bp)) and attenuation CT acquisition.

Patient group	Delay in minutes (≈)	Amount of FDG after delay (%)	Correction factor	Second PET, scan time per bp (s)	Second PET/CT scan time (min)
1	21	88%	1.14	60*1.14 = 68	18
2	32	82%	1.22	120*1.22 = 147	32
3	36	80%	1.25	60*1.25 = 75	19
4	47	74%	1.34	120*1.34 = 161	35

To provide an optimal comparison between conventional and digital PET/CT, we will use a patient-specific protocol for the second PET scan, based on the exact delay for each patient. This delay will be determined once the patient arrives in the room for the second PET/CT scan and will be used to set the final PET scan time per bed position for the second PET scan, for each patient separately.

#### **5.1.5 PET/CT data reconstruction**

For both conventional and digital PET/CT, the attenuation correction of PET images is based on CT attenuation maps. For the conventional PET/CT study, images will be reconstructed using standard clinical Isala protocol. This protocol includes two types of reconstructions: one reconstruction method fulfilling EANM guidelines for FDG-PET tumor imaging and one reconstruction method for optimal lesion detection using small 2x2x2 mm^3 voxels [7].

Digital PET/CT images will initially be reconstructed using a protocol advised by the vendor. However, in retrospective we may perform several additional reconstructions on the PET/CT scans obtained during this study. This will be done to determine and evaluate for example optimal settings for image quality, lesion detectability and clinical performance. This will also include the reconstruction fulfilling EANM guidelines for FDG-PET tumor imaging.

#### **5.1.6 PET/CT diagnoses**

Diagnoses will be made from images acquired on both the conventional and digital PET/CT system. The images acquired from the digital PET/CT scan will be included in the patients' medical record. The nuclear medicine physician will mention differences between the analog and digital PET in the PET/CT report, and the referring physician can discuss this with the patient.

## 5.2 Data collection and analysis

### 5.2.1 General data collection

For each patient, we will collect several patient- and scan characteristics as presented in Figure 5.

Patient characteristics	
Date of birth	dd-mm-jjjj
Gender	Male/female
Diabetes	Yes / no / unknown
Length (cm)	.....
Weight (kg)	.....
Glucose (mmol/L)	.....
Directed by	Zwolle, Meppel, etcetera.
Indication	Staging / restaging / other / unknown

PET-scan parameters		CT-scan parameters	
PET/CT scanner	Ingenuity / Digital PET	mA	.....
Date of PET scan	dd-mm-jjjj	kV	.....
Time of FDG administration	.....	Idose	Yes / no
Start scan time	.....	CTDI (mGy)	.....
Netto activity (MBq)	.....	DLP (mGy * cm)	.....
Number of bed positions	.....		
Time per bed position (min)	.....		
PSF modulation	Yes / no		
Reconstruction voxel size	4 mm, 2 mm		

**Figure 5:** Description of patient- and scan characteristics that will be collected for this study.

For each patient, we will start with an analysis of both conventional and digital PET/CT images separately. One investigator will evaluate the PET/CT images quantitatively while two NM physicians will give qualitative (visual) judgments. When both conventional and digital PET/CT images from a patient are evaluated separately, the results will be compared and differences between the image datasets will be identified.

We will focus on PET/CT based TNM staging, which includes evaluation of the primary tumor, regional lymph nodes and distant metastasis. This means that for patients with (suspected) lung cancer, we will focus on the evaluation of primary lung tumor(s), mediastinal and hilar lymph nodes and distant metastases (in particular adrenal glands). For patient with (suspected) breast cancer, we will focus on the analysis of primary breast tumors, regional lymph nodes (axillary, subclaviculair, internal mammary and supraclavicular) and distant metastases. In patients suspicious for esophageal cancer, we will focus on the primary esophageal tumor, regional lymph nodes in the thorax and lower abdomen, and distant metastasis. Furthermore, other (rather unexpected) findings and differences between conventional and digital PET imaging will be studied and documented.

## **5.2.2 PET/CT evaluation**

### **Quantitative evaluation**

The following general measurements will be performed on all PET images:

- Liver noise level
- Lung noise level
- Normal tissue uptake (SUVmean and SUVmax) in both lungs, blood pool, liver, both adrenal glands, spleen, bones and bone marrow.

For all lesions, the following measurements will be performed on PET images:

- SUVmax
- SUVmean (based on 50% SUVmax)
- Volume om mL (based on 50%SUVmax)
- Lesion contrast
- Lesion contrast-to-noise
- Lesion-to-liver ratio
- Lesion-to-aorta ratio

Furthermore, the lesion diameter as measured on the attenuation CT scan will be collected to make stratifications based on lesion diameter.

### **Qualitative (visual) evaluation**

Visual assessment of conventional and digital PET images will be performed by two NM physicians, blinded for patient characteristics and patient history. They perform a general evaluation for:

- PET image quality (4-point scale: poor, fair, good, excellent)
- Liver noise (4-point scale: low, mild, moderate, high)
- Lung noise (4-point scale: low, mild, moderate, high)
- Assessment of any visible artifacts, occurrence of distortion or any other visual impressions

Moreover, each selected lesion will be visually evaluated on both PET datasets using a 4-point scale:

1. No visualization
2. Mild intensity
3. Moderate intensity
4. High intensity

Moreover, the NM physicians will both judge each lesion on a 4-point scale (definitely benign, likely benign, likely malignant, definitely malignant) on both

datasets separately. This is used for performance evaluation in lesion characterization, and to compare the diagnostic confidence.

Finally, the adrenal glands are visually assessed using the following 4-point scale:

1. Uptake below liver uptake
2. Uptake equal to liver
3. Uptake slightly greater than liver uptake
4. Uptake much greater than liver uptake

To reduce the impact of a potential learning effect for reading digital PET images, we will randomize the reading order for both NM physicians.

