### **3. STUDY DESIGN**

We will perform a single center diagnostic accuracy study, in which patient-scans obtained using two types of PET/CT scanners (1 clinical study on the conventional system and 1 clinical study on the digital system) will be intra-individually compared.

Patient selection will be performed at the NM department in Isala. Patient eligibility will be based on the information provided by the referring specialist on the requisition for the clinical FDG-PET/CT study.

Patients will be included during the inclusion period of 6-12 months. Patients that meet the inclusion criteria and have signed informed consent will undergo two PET/CT scans on both the conventional and the digital PET system, immediately after each other. The scan order will be randomized per week:

- Week 1: first scan on conventional PET/CT, second scan on digital PET/CT.
- Week 2: first scan on digital PET/CT, second scan on conventional PET/CT. Etc.

For each patient, we start with a separate analysis of conventional and digital PET/CT images. One investigator will evaluate the PET/CT images quantitatively while two NM physicians will give qualitative (visual) judgments. Afterwards, we compare conventional and digital findings for all patients.

PET/CT data will be analyzed based on three subgroups of patients with lung cancer, breast cancer and esophageal cancer respectively. Pathology results and follow-up imaging by PET, CT, echography and MRI will be used as gold standard. When validation results are not available, conventional and digital PET/CT results are just compared with each other. More information on data analysis is described in section 5.2.

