#### 4.4 Sample size calculation

From the detailed research questions stated in chapter 2, a rough estimate of the number of required subjects will be calculated, although this is difficult because the clinical performance parameters for digital PET are not available yet. The only qualitative impression from preliminary images is that image quality and detection properties are going to be significantly better.

Sample size calculations are performed for primary objectives 1.1 and 1.3. We do not formally calculate estimates for the remaining objectives, but estimate that there will be ample scans to answer these objectives, once the first questions have been answered. Furthermore in general, we expect that around 10% of the patients that are included in this study show a negative PET/CT scan, without the presence of malignant disease. Therefore, we will increase the required number of patients with 10%, to reach the required number of patients with malignancies for this study.

The sample size calculation is performed for the three subgroups of cancer types separately. However, the sample size calculation for patients with lung cancer and patients with breast cancer is identical, due to a roughly comparable disease incidence (and thus a comparable amount of FDG-PET/CT scans acquired) and a comparable expected performance. For esophageal cancer, a separate sample size calculation is provided, due to a lower disease incidence.

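### The plan does not specify masking the two readers to the scanner or a minimum interval between a patient's two reads, so the reader-based primary outcome is open to expectation bias and carry-over

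*Combined protocol and SAP*

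**What the plan says.** Under Qualitative (visual) evaluation in section 5.2.2, the two readers are "blinded for patient characteristics and patient history". That is the only blinding stated. Scanner name, image header and scan order are not mentioned.

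Two safeguards are given. Section 3 says that for each patient "we start with a separate analysis of conventional and digital PET/CT images", with comparison afterwards, and section 5.2.1 repeats this. Section 5.2.2 adds: "To reduce the impact of a potential learning effect for reading digital PET images, we will randomize the reading order for both NM physicians". Neither comes with a minimum interval between the two reads of one patient.

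For visibility scoring, "each selected lesion will be visually evaluated on both PET datasets using a 4-point scale", and one of the four grades is for a lesion that is not seen. Who selects the lesions, and from which scan, is not stated.

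The same two physicians give the final diagnostic outcome (Inter-observer agreements, end of section 7.1.2), and sensitivity, specificity and accuracy are computed for each of them (section 7.1.1). Section 7.1 counts every disagreement in T, N or M stage as a difference.

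Two other places bear on what a reader may expect or know. Section 4.4 reports an impression from preliminary images that "image quality and detection properties are going to be significantly better". Section 5.1.6 says: "The nuclear medicine physician will mention differences between the analog and digital PET in the PET/CT report".

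**The concern.** Comparing scanners within the patient removes differences between patients. That leaves reader judgement as a main route by which bias can enter, and the lesion counts, the N and M status and the TNM class are all reader judgements. Two mechanisms are left open, and they act in opposite directions.

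- **Expectation.** A reader who knows which scanner produced the image, and expects digital to show more, may resolve equivocal nodes upward on digital. This happens whichever scan is read first, so randomising the order does not cancel it.
- **Carry-over.** A reader who remembers the first scan may repeat its call on the second. Randomised order balances which scanner benefits, but the two reads are still drawn together and true differences are diluted.

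A positive result could then not be cleanly separated from expectation, nor a null result from recall. Kappa between the two readers would not reveal a tendency that they share.

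**Working it through.** **1. The plan's own figures.** In an exact two-sided sign test on n non-tied patients, let c be the smallest count with 2·P(X ≥ c | n, 0.5) ≤ α. Power is P(X ≥ c | n, 0.5 + d), where d is the stated difference from section 4.4. The smallest n that reaches the target power is:

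| Objective and group | d | α | target power | n found | n stated | c | exact power |
|---|---|---|---|---|---|---|---|
| 1.1 lung, breast | 0.20 | 0.05 | 80% | 49 | 49 | 32 | 81.0% |
| 1.3 lung, breast | 0.16 | 0.05 | 80% | 79 | 79 | 49 | 80.7% |
| 1.1 esophageal | 0.20 | 0.10 | 65% | 28 | 28 | 19 | 68.2% |
| 1.3 esophageal | 0.16 | 0.10 | 65% | 42 | 42 | 27 | 66.0% |

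All four reproduce, so this is the right test model. The n here counts patients whose two scans differ. Masking would not change these sample sizes.

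**2. Expectation, with no true difference.** The inputs below are assumptions, because the documents give neither discordance rates nor the size of any lean.

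- Without a lean, a share b of patients is called higher on each scanner: b = 5% or 10%.
- Knowing the scanner adds a lean L of patients called higher on digital. So p₊ = b + L, p₋ = b, the discordant share is π = p₊ + p₋, and the digital share of discordant patients is q = p₊/π.
- P(significant) = Σₘ Bin(m; N, π) · [P(X ≥ cₘ | m, q) + P(X ≤ m − cₘ | m, q)], with cₘ taken at two-sided 0.05, the threshold in section 7.1.1.

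Example with N = 90, b = 5%, L = 5 points: p₊ = 0.10, p₋ = 0.05, π = 0.15 (13.5 discordant patients expected), q = 0.667, and the result is 15.6%. With b = 10%: p₊ = 0.15, p₋ = 0.10, π = 0.25, q = 0.60, and the result is 10.9%.

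| Lean L (points) | N = 45 | N = 90 |
|---|---|---|
| 0 | 0.7-2.1% | 2.0-2.9% |
| 1-2 | 1.0-2.7% | 2.7-4.4% |
| 5 | 5.6-5.8% | 10.9-15.6% |
| 10 | 15.6-20.7% | 33.3-49.4% |

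Ranges run over b = 5% and 10%. If all 225 patients were tested together, 5 points would give 28.0-42.4% and 10 points 75.8-91.5%. However, section 4.4 sizes the study by tumour type (90, 90 and 45), and section 3 says the data are analysed that way.

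**3. Carry-over, with a true difference.** Take the planned effect for objective 1.3, a 66:34 split, and suppose that recall turns discordant pairs into ties without changing the split (an assumption). Exact power at two-sided 0.05 is 80.7% with 79 discordant patients, 60.6% with 49, 49.4% with 40 and 40.1% with 30. Losing 30 of 79 pairs (38%) would cost about 20 points of power (80.7 − 60.6).

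**The case against.** Several points on the other side have force.

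- **Silence is not a statement.** A reader might infer that the physicians are unmasked to the scanner. The plan does not say so; masking is simply not specified, and it may be intended.
- **Safeguards exist.** The scans are analysed separately before comparison, the benign or malignant call is made on each dataset separately, and "we will randomize the reading order for both NM physicians". If all scans are randomly mixed, a patient's two reads could already fall well apart. This reduces carry-over and balances its direction, but it does not touch expectation, and no interval is guaranteed.
- **The lesion list.** A reader might infer that a shared list biases N status and lesion counts. A common list is a fair inference from scoring the same lesions on both datasets with a grade for non-visualisation. But it is described for visibility and for benign or malignant scoring; no section ties objectives 1.1 to 1.7 to it.
- **The clinical report.** A reader might infer that the reporting physician is also a study reader. Section 5.1.6 does not say that, and blinding to patient history arguably covers the report.
- **Direction.** A reader might infer an overall bias toward digital. Only the missing scanner mask points that way. The remark in section 4.4 is a hedged impression in a sample-size section, and the primary question in section 2.1 is two-sided.
- **Reference standard.** Over-calling on digital should add false positives and lower its specificity in objective 1.8. This is a useful check but a partial one, since section 3 accepts that validation will not be available for every patient.
- **Assumed lean.** At 1-2 points and n = 90 the false-significance rate stays below 5%. At n = 45 even 5 points gives only about 6%.

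What remains is that neither scanner masking nor an interval is written into the plan, and nothing else in it removes expectation.

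**Conclusion.** The point holds in limited form. Scanner masking and a minimum interval between a patient's two reads are not specified, and the same two readers produce the primary outcome. That outcome may be biased toward digital PET by expectation and toward agreement by carry-over. The net direction and size cannot be found from the documents.

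The figures are illustrations. They rest on an assumed 5-10% discordance each way and an assumed lean. The lean is harmless at 1-2 points with n = 90. It matters at 5 points (11-16% false significance) and is serious at 10 (33-49%). In the group of 45 the figures are about 6% and 16-21%. The change is cheap and should be made before the study reads begin. If practice already follows it, the plan should say so.

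**What to change.** In section 5.2.2, state that:

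1. scanner name, header data and scan order are removed from images used for study reads;
2. a patient's two scans are read in separate sessions with a stated minimum interval (for example 4 weeks, which is a judgement and has no basis in the documents), keeping the randomised reading order;
3. on each scan, lesions are identified and the TNM call is locked independently before the other scan is opened, and only then are lesions matched for the visibility and benign or malignant scoring;
4. study reads are kept blind to the comparative clinical report of section 5.1.6, or separated from it by the same interval, and the plan says whether a study reader may also write that report.

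Item 3 largely formalises the separate analysis already planned. Items 1 and 4 and the interval in item 2 are new. The cost is anonymisation work and calendar time, with no added patient, scan or reader and no change in sample size. Masking will be partial because image texture may reveal the scanner, and the report should acknowledge this.

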### **5.2.3 Validation**

For each patient, the results of the PET/CT studies will be compared with available validation results. It is preferred that this regards invasive staging with pathology (PA) evaluation, although it may also include follow-up or information from other imaging modalities such as MRI and contrast-enhanced CT. Validation shall be performed based on findings from both conventional and digital PET/CT.

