Furthermore, in the past few years procedure guidelines for FDG-PET tumor imaging were published by the European Association of Nuclear Medicine (EANM) to provide a minimum standard for the acquisition and interpretation of FDG-PET/CT scans [6]. These common standards are useful for quantification, valuable for response monitoring and increasingly used in multi-center trials. For the digital PET/CT system, acquisition- and reconstruction settings to fulfill these procedure guidelines yet need to be determined. Both calibration and validation of various system settings will be done in this study.

In the current study we will focus on three specific patients groups; patients with (suspected) lung cancer, breast cancer and esophageal cancer. There are multiple reasons for choosing these three patients groups for the present study:

1. FDG-PET/CT imaging is frequently used in these patient groups and has importance for diagnosis and disease staging.
2. In many cases within these groups, invasive staging procedures are performed in our hospital after PET/CT acquisition. This provides validation material that can be used to compare the clinical performance of conventional and digital PET/CT.

3. The disease incidence for these three cancer types is fairly high, providing the opportunity to reach a large enough study population within the selected period.
4. In these cancer types, the areas of nodal metastases are the mediastinum, the axillae and the upper abdomen. In this way we will obtain a fairly complete impression of PET staging properties in a large proportion of relevant tissue areas.

With the inclusion of these three patients groups, we will be able to make a comparison of conventional and digital PET/CT for these specified groups. However, we expect that such findings can be extrapolated to obtain an impression of the general clinical impact of digital PET/CT in all patients with cancer. Possibly the data from this study can be used to identify specific clinical areas where the digital technology may outperform conventional PET technology. Such initial data may be used to plan specific, hypothesis-driven follow-up studies to support performance and clinical claims for digital PET in general.

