#### 7.1.1 Primary objective: diagnostic outcome of the PET/CT studies

For each patient separately, the diagnostic outcome for the conventional and digital PET/CT study will be compared. Measured ordinal differences in for example the N-status or the TNM classification will be assessed based on two methods. The first method is based on the sign test, in which the comparison results in an agreement or a disagreement. The second method is based on the Wilcoxon signed-ranked test, in which the amount of disagreement is also taken into account. Moreover, we will calculate agreement percentages on the diagnostic outcome between both systems. Furthermore, using validation results as a reference, we will determine the sensitivity, specificity and accuracy for both NM physicians based on the following formulas:

$$\text{Sensitivity} = N_{PET \text{ positive}} / N_{\text{true positive}}$$

$$\text{Specificity} = N_{PET \text{ negative}} / N_{\text{true negative}}$$

$$\text{Accuracy} = (N_{PET \text{ positive}} + N_{PET \text{ negative}}) / (N_{\text{true positive}} + N_{\text{true negative}})$$

To test whether differences in sensitivity, specificity and accuracy between conventional and digital PET/CT are significant, we will apply the McNemar paired proportion test. A p value of less than 0.05 will be considered to indicate statistical significance.

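### No rule covers reference results for sites negative on both scans, so absolute sensitivity and specificity are open to partial-verification bias and any true specificity difference may be enlarged

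*Combined protocol and SAP*

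**What the plan says.** Objective 1.8 (section 2.1) asks for sensitivity, specificity and accuracy of the two scanners against a composite reference standard. Four parts of the plan determine which cases can contribute.

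- **Where validation comes from.** Section 5.2.3: "Validation shall be performed based on findings from both conventional and digital PET/CT". The same section limits it to what exists: "For each patient, the results of the PET/CT studies will be compared with available validation results".
- **What counts as validation.** Section 5.2.3: "It is preferred that this regards invasive staging with pathology (PA) evaluation, although it may also include follow-up or information from other imaging modalities". Section 3 is similar: "Pathology results and follow-up imaging by PET, CT, echography and MRI will be used as gold standard".
- **Cases without validation.** Section 3: "When validation results are not available, conventional and digital PET/CT results are just compared with each other".
- **The analysis.** Section 7.1.1: "using validation results as a reference, we will determine the sensitivity, specificity and accuracy for both NM physicians". For differences between scanners, "we will apply the McNemar paired proportion test", at the 0.05 level.

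Section 5.1.6 places the digital images in the medical record and has differences between the scans reported, so a positive result on either scanner can prompt work-up. Section 9.5 ends the study at inclusion of the 225th patient, and no section sets a follow-up window for the reference standard. Nothing in section 7 deals with partial verification.

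**The concern.** Sites negative on both scans supply the disease that both scanners miss, which belongs in both sensitivity denominators. They also supply most of the true negatives. If they reach the accuracy analysis less often than sites positive on at least one scan, the verified sample is enriched for positive results. Both sensitivities then look too high and both specificities too low.

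Pairing does not remove this from the reported differences. Both scanners share a denominator that has shrunk, so each absolute difference is scaled up. The effect is largest for specificity, because most non-diseased sites are negative on both scans.

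At stake is how extra true detections on digital PET are weighed against extra false positives. Section 9.6 says the results may support marketing and regulatory claims, so the size of a specificity loss matters as well as its direction.

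**Working it through.** **Inputs.** The plan gives no accuracy values and no verification rates, so there is no figure of its own to reproduce here. The sign-test sample sizes in section 4.4 serve objectives 1.1 and 1.3 and do not enter. All values below are assumptions. I read the formulas in 7.1.1 as the usual definitions.

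| Assumed paired result | Diseased sites | Non-diseased sites |
|---|---|---|
| Positive on both | 0.70 | 0.05 |
| Conventional only | 0.05 | 0.03 |
| Digital only | 0.15 | 0.07 |
| Negative on both | 0.10 | 0.85 |

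True sensitivity is therefore 0.75 conventional and 0.85 digital. True specificity is 1 − 0.08 = 0.92 and 1 − 0.12 = 0.88. Either-positive sites are verified with probability v+ = 0.8, both-negative sites with probability v−.

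**Formulas among verified sites.**
- Observed sensitivity = v+ × true sensitivity / (0.90 v+ + 0.10 v−)
- Observed false-positive rate = v+ × true false-positive rate / (0.15 v+ + 0.85 v−)

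**Worked case, v− = 0.10.**
- Diseased denominator: 0.72 + 0.01 = 0.73. Sensitivity: 0.60/0.73 = 82% and 0.68/0.73 = 93%. Difference: 0.08/0.73 = 11 points.
- Non-diseased denominator: 0.12 + 0.085 = 0.205. Specificity: 1 − 0.064/0.205 = 69% and 1 − 0.096/0.205 = 53%. Difference: 0.032/0.205 = 16 points.

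**Range.**

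| v− | Sensitivity, conv. / digital | Difference | Specificity, conv. / digital | Difference |
|---|---|---|---|---|
| 0.80 (equal rates) | 75.0% / 85.0% | +10.0 | 92.0% / 88.0% | −4.0 |
| 0.50 | 77.9% / 88.3% | +10.4 | 88.3% / 82.4% | −5.9 |
| 0.10 | 82.2% / 93.2% | +11.0 | 68.8% / 53.2% | −15.6 |
| 0.05 | 82.8% / 93.8% | +11.0 | 60.6% / 40.9% | −19.7 |

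**What does not move.** The two scanners share each denominator, so it cancels from the ratios. The true-positive ratio is 0.68/0.60 = 1.13 and the false-positive ratio 0.096/0.064 = 1.50 in every row, equal to the true 0.85/0.75 and 0.12/0.08. McNemar uses discordant pairs only, and a both-negative site is never discordant.

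**Second set of assumptions.** Take sensitivity 0.70 and 0.80, specificity 0.90 and 0.85, within-site correlation 0.6, v+ = 0.9 and v− = 0.2. The sensitivity difference goes from +0.10 to +0.115 and the specificity difference from −0.05 to −0.141. The ratios stay at 1.143 and 1.50. With both true specificities at 0.90, the observed specificities are both 0.695 and the difference remains 0. The accuracy difference goes from +0.010 to +0.018 at site prevalence 0.4 and from −0.020 to −0.044 at prevalence 0.2: rescaled, with the sign kept.

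**When the ratios fail.** Return to the first set of cells and verify both-positive sites at 0.9, conventional-only at 0.7 and digital-only at 0.5.
- True-positive ratio: (0.63 + 0.075)/(0.63 + 0.035) = 0.705/0.665 = 1.06, not 1.13.
- False-positive ratio: (0.045 + 0.035)/(0.045 + 0.021) = 0.080/0.066 = 1.21, not 1.50.
- Digital-only to conventional-only among diseased sites, which drives McNemar: 0.075/0.035 = 2.1, not 0.15/0.05 = 3.0.

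**The case against.** A reader might infer that both-negative sites will rarely be verified. The documents do not say so. They give no rate, and several provisions could supply reference results for negative sites:

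- Sections 3 and 5.2.3 admit follow-up and other imaging.
- Section 5.1.3 says many patients also have a diagnostic contrast-enhanced CT.
- Section 1 notes: "In many cases within these groups, invasive staging procedures are performed in our hospital after PET/CT acquisition". It does not confine that staging to PET-positive sites.
- Section 5.2.3 speaks of findings, not positive findings, and readers in 5.2.2 may grade a lesion as benign. Using both scanners' findings also protects against verifying only one scanner's positives.

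All of this stands, and the point is therefore conditional. None of it amounts to a rule: these sources are permitted, not required or scheduled.

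A reader might also infer that the whole paired comparison is invalid. That goes too far. Under equal verification of either-positive sites the distortion is a rescaling, the planned test is untouched and the sensitivity difference barely changes.

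Finally, the reach is limited. Objectives 1.1 and 1.3, the only ones with a sample size, need no reference standard. Objective 1.8 is not the sole check on whether findings are correct, since objective 2.5 also uses validation results. Section 1 presents the study as an initial assessment.

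**Conclusion.** The point holds as a conditional risk. The plan links verification to PET findings, analyses only what is verified, and has no provision for sites negative on both scans. If those sites are verified less often than either-positive sites, absolute sensitivity is too high, absolute specificity too low, and a true specificity difference is enlarged. Under the assumed cells, a 4-point loss appears as about 6 to 20 points as v− falls from 50% to 5%, against v+ of 80%. At equal rates there is no bias, and if the true specificities are equal the difference stays zero.

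The preservation of sign, null, ratios and McNemar rests on one further assumption: that conventional-only, digital-only and both-positive sites are verified at the same rate. The plan neither ensures nor excludes this. The documents support neither a claim that both-negative sites go largely unverified nor a claim that McNemar's test fails as planned.

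**What to change.** Amend section 7.1.1 as follows.

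1. Make the ratios of true-positive and of false-positive rates (digital / conventional), with 95% confidence intervals among verified cases, the main accuracy comparison. Keep McNemar on the discordant verified pairs.
2. State that the ratios and McNemar assume equal verification of both-positive, conventional-only and digital-only sites.
3. Tabulate the number and share verified for each of the four paired results. The both-negative row needs a countable denominator, so fix the list of nodal stations and organ systems to be scored for each cancer type beforehand.
4. If verification differs among the three either-positive groups, add a sensitivity analysis that reweights by the observed rates.
5. Label absolute sensitivity, specificity and accuracy as conditional on verification. Alternatively, give bounds or a verification-bias correction (Begg-Greenes or multiple imputation), noting that the usual correction assumes verification depends only on recorded results.

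The cost is SAP wording, one extra table and a short sensitivity analysis, with no extra patient procedures. The downside is that absolute accuracy is no longer a headline result.
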